4.1.2 Secondary Endpoints

Pharmacokinetics and Immunogenicity:

- 1. Potency and breadth of HIV neutralization activity on a standard HIV panel
- 2. Level of PG9 serum antibody
- 3. Level of anti-PG9 serum antibodies
- 4. Level of anti-AAV1 antibodies
- 5. Proportion of volunteers with detectable AAV1 in blood (by RT-PCR) in each group
- 6. AAV1-specific T cell responses

5.0 STUDY DESIGN

The study is a Phase 1 randomized, placebo-controlled, double-blind, dose-escalation clinical trial in healthy male adult volunteers to evaluate the safety and expression of a single intramuscular administration of rAAV1-PG9DP at $4x10^{12}vg$, $4x10^{13}vg$, $8x10^{13}vg$ and $1.2x10^{14}vg$.

Sentinel recipients

The rAAV1-PG9DP administrations escalate by dosage as shown below in Table 1, Study Design. In Groups A-D, the first 3 volunteer injections will be separated by 7 days, to allow for observation of IMP-related adverse events in the first two participants. Because there is one placebo in each group, the first two recipients will be treated as sentinel recipients (at least one will receive the IMP). If no reactogenicity and adverse events that are considered to be related to IMP (possibly, probably or definitely related) and are graded as severe or worse (Grade 3 or 4 on the DAIDS Toxicity Table) occur within 7 days after injection, the second volunteer may be injected. The same process will be followed after the second injection. If no events meeting the criteria described above occur within 7 days after the second volunteer is injected, then the

above do occur for the first two volunteers, they will be reviewed by the Safety Review Board (SRB) to determine whether further injections may proceed.

Dose escalation

Once all volunteers in the first dosage group (Group A) have received their injection, enrolment into the next higher dosage group / assignment of new allocation numbers will pause. Safety data through the Day 42 post-injection visit for all volunteers in the dosage group will be reviewed by the SRB prior to allowing volunteers into the second dosage group (Group B). Specific safety criteria to allow dose escalation are detailed in Section 17.2.2. If criteria for dose escalation are met, Group B enrolment will proceed. Once safety data through Day 42 post-injection visit is available for all volunteers in Group B, all available safety data (Groups A and B) will be reviewed by the SRB prior to allowing volunteers into Group C. If criteria for dose escalation are met, Group C enrolment will proceed. Once safety data through Day 56 post-injection visit is available for all volunteers in Group C, all available safety data (Groups A, B and C) will be reviewed by the SRB. In addition, PG9 antibody expression will be evaluated.

- If safety criteria to allow dose escalation are met and PG9 antibody expression is sufficient (~150ug/ml), the study will proceed to enrol an expanded number of volunteers at the Group C dose (Group C1) and enrolment into Group D will not occur.
- Otherwise, if PG9 antibody expression is not sufficient but safety criteria for dose escalation are met, the study will proceed to enrol the highest dose level (Group D). Safety and tolerability will be evaluated by the SRB over at least 56 days for volunteers in Group D. Once safety data through Day 56 post-injection visit is available for all volunteers in Group D, all available safety data (Groups A, B, C and D) will be reviewed by the SRB. If criteria for dose escalation are met, the study will proceed to enrol an expanded number of volunteers at the Group D dose (Group D1).

In the study all groups will be randomized in a 3:1 ratio of active product to placebo with the exception of Group D1, where 5 volunteers will be randomized in a 4:1 ratio of active product to placebo.

Table 5.0-1 Study Design

	Number Active/						
Group	Placebo	Dose (vg)	Route	Month 0			
А	3/1	4x10 ¹² or Placebo	IM	х			
SRB revie	SRB review						
в	3/1	4x10 ¹³ or Placebo	IM	х			
SRB review							
с	3/1	8x10 ¹³ or Placebo	ІМ	x			
SRB review to determine progression to either C1, or D and D1							
C1	9/3	8x10 ¹³ or Placebo	IM	х			
Total Number of Volunteers: 24 (18/6)							
OR							
D	3/1	1.2x10 ¹⁴ or Placebo	IM	Х			
SRB review							
D1	4/1	1.2x10 ¹⁴ or Placebo	IM	Х			
Total Number of Volunteers: 21 (16/5)							

IM=Intramuscular

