6.2 Injection Visit

Prior to the injection, study staff will:

- Answer any questions the volunteer may have about the study
- Review the Informed Consent Document with the volunteer
- Review screening safety laboratory data
- Conduct HIV risk assessment
- Conduct HIV testing, HIV test counselling and HIV risk reduction counselling
- Review interim medical history
- Collect concomitant medication information
- Perform a symptom-directed physical examination (refer to Section 7.2)
- Assess cervical and axillary lymph nodes
- Prior to injection, assess local and systemic signs and symptoms (this includes an examination of injection site)
- Collect specimens as indicated in Section 9.1.10
- Perform ECG
- Assign an allocation number to the volunteer according to the instructions specified in the Study Operations Manual (SOM)

Administer the IMP as specified in Section 8.4, Administration of IMP and according to the instructions specified in the SOM.

Observe volunteer closely for at least 30 minutes and then for a total of 4 hours after injection for any acute reactogenicity and symptoms of anaphylaxis.

At the end of each observation period, or if any clinical signs of adverse reactions are observed, study staff will:

- Record vital signs (pulse, respiratory rate, blood pressure and temperature)
- Assess any local and systemic reactogenicity
- Assess any other adverse events

6.3 **Post-Injection Visits**

The volunteer will be asked to return to the clinic on Day 3 (+/- 1 day), Day 7 (+/- 3 days), Day 14 (+/- 3 days), Day 21 (+/- 3 days), Day 28 (+/- 3 days), Day 35 (+/- 3 days), and Day 42 (+/- 3 days) after injection for an assessment by clinic staff. The volunteer will be asked to maintain a Memory Aid from the day of the injection and for the next 7 days. Study staff will review the Memory Aid with the volunteer and determine the severity of the reactions through discussion with the volunteer.

The following procedures will be conducted at these visits:

- Review interim medical history
- Collect concomitant medication information
- Perform a symptom-directed physical examination if any signs or symptoms are present
- Assess cervical and axillary lymph nodes
- Assess local and systemic reactogenicity (Days 3 and 7 only)
- Assess any adverse events
- Collect specimens as indicated in the Schedule of Procedures (Appendix A)
- Perform ECG

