9.1.10 Routine laboratory parameters (Safety Labs)

Table 9.1.10-1 shows the laboratory parameters that will be measured routinely. The samples for these tests will be collected at Screening and all subsequent visits, as indicated in the Schedule of Procedures (Appendix A). Note that the Day 3 (+/- 1 day) visit does not include total bilirubin, alkaline phosphatase, albumin, creatine kinase and all tests listed in Table 9.1.10-1 as "Other". Also note that the Day 49 and Day 70 safety labs include Cardiac Troponin I only.

Laboratory	Test
Parameter	
Haematology	Haemoglobin, haematocrit, leukocytes, platelets, absolute neutrophil count, absolute lymphocyte count
Clinical	Sodium, potassium, creatinine, aspartate aminotransferase (AST),
Chemistry	alanine aminotransferase (ALT), total bilirubin, alkaline
	phosphatase, albumin, creatine kinase,
Urinalysis	Dipstick test for protein, blood glucose, ketones, esterase (leukocytes) and nitrite. If clinically significant abnormalities (e.g. blood, protein, leukocytes) are found on dipstick test, then further test(s) will be performed (e.g. microscopy, culture).
Other	C-reactive protein, cardiac troponin I, aPTT, INR, complement C3 and C4

 Table 9.1.10-1: Laboratory Parameters

9.1.11 Specific screening tests:

In addition to the tests listed in the table above, Screening Labs will include:

- Anti-AAV1 and anti-AAV2 antibodies
- PG9 antibodies
- Gamma glutamyl transferase (GGT)

In addition, volunteers will be screened to exclude the following diseases:

- Hepatitis B: positive for hepatitis B surface antigen (HBsAg)
- Hepatitis C: positive for hepatitis C antibodies (HCV antibodies)
- Active syphilis: confirmed diagnosis (i.e., positive RPR confirmed by TPHA)

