10.0 ADVERSE EVENTS

10.1 Definition

An adverse event (AE) is any untoward medical occurrence in a volunteer administered IMP and which does not necessarily have a causal relationship with the IMP. An AE can therefore be any unfavorable or unintended sign (including an abnormal laboratory finding), symptom, or disease, temporally associated with the use of the IMP whether or not related to the IMP.

Assessment of severity of all AEs, including expectedness and seriousness of AEs, is ultimately the responsibility of the Principal Investigator.

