17.4 Criteria for Pausing the Study

Enrolments and injections will be paused, a formal study halt will be submitted to the MHRA as a substantial amendment, and a safety review conducted by the SRB for any of the following criteria:

- 1. One volunteer develops a Grade 3 or 4 adverse event that is judged to be possibly, probably or definitely related to IMP;
- 2. Grade 2 adverse events that persists for more than 7 days that is possibly, probably or definitely related to the IMP;
- 3. One volunteer experiences a serious adverse event that is probably or definitely related to the IMP, or two or more subjects experience similar serious adverse events which are possibly related to the IMP;
- 4. There is a volunteer death assessed as possibly, probably or definitely related to the IMP;
- 5. One volunteer shows evidence of disease that might be due to immune complexes and is judged to be possibly, probably or definitely related to IMP, such as acute arthritis, severe generalized rash, or glomerulonephritis;
- 6. A 5-fold increase in ALT within 10 weeks after IMP administration which is not responsive to oral corticosteroids and is judged to be possibly, probably or definitely related to IMP.

The Sponsor will request a review by the SRB, (or the SRB chair if other SRB members cannot be convened), to be held within 2 business days of the Sponsor learning of the

event. The individual volunteer(s)/or study may be unblinded at the discretion of the SRB.

Following this review, the SRB will make a recommendation regarding the continuation or suspension of the vaccinations or the trial and communicate this decision immediately to the Sponsor. If the SRB decision is to restart enrolments and injections, then a further substantial amendment will be submitted to the MHRA including all appropriate safety data and justification to restart. The Sponsor then will inform the Principal Investigator of the MHRA decision.

Additional *ad hoc* review may be specifically requested by the Sponsor, the Principal Investigator(s) or by the SRB.

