Comment: Some laboratori same tests; values should b Bilirubin (Total)	e graded according to the i	ranges for Bicarbonate as lis	sted above.	
Adult and Pediatric > 14 days	1.1 – 1.5 x ULN	1.6 – 2.5 x ULN	2.6 – 5.0 x ULN	> 5.0 x ULN
Infant* [†] , ≤ 14 days (non-hemolytic)	NA	20.0 – 25.0 mg/dL 342 – 428 µmol/L	25.1 – 30.0 mg/dL 429 – 513 μmol/L	> 30.0 mg/dL > 513.0 µmol/L
Infant* [†] , ≤ 14 days (hemolytic)	NA	NA	20.0 – 25.0 mg/dL 342 – 428 μmol/L	> 25.0 mg/dL > 428 µmol/L
Calcium, serum, high				
Adult and Pediatric ≥ 7 days	10.6 – 11.5 mg/dL 2.65 – 2.88 mmol/L	11.6 – 12.5 mg/dL 2.89 – 3.13 mmol/L	12.6 – 13.5 mg/dL 3.14 – 3.38 mmol/L	> 13.5 mg/dL > 3.38 mmol/L
Infant* [⁺] , < 7 days	11.5 – 12.4 mg/dL 2.88 – 3.10 mmol/L	12.5 – 12.9 mg/dL 3.11 – 3.23 mmol/L	13.0 – 13.5 mg/dL 3.245 – 3.38 mmol/L	> 13.5 mg/dL > 3.38 mmol/L
Calcium, serum, low			6.1 – 6.9 mg/dL	< 6.1 mg/dL
Calcium, serum, low Adult and Pediatric ≥ 7 days	7.8 – 8.4 mg/dL 1.95 – 2.10 mmol/L	7.0 – 7.7 mg/dL 1.75 – 1.94 mmol/L	1.53 – 1.74 mmol/L	< 1.53 mmol/L

LABORATORY				
PARAMETER	GRADE 1 MILD	GRADE 2 MODERATE	GRADE 3 SEVERE	GRADE 4 VERY SEVERE
Cardiac troponin I (cTnI)	NA	NA	NA	Levels consistent with myocardial infarction or unstable angina as defined by the manufacturer
Cardiac troponin T (cTnT)	NA	NA	NA	≥ 0.20 ng/mL OR Levels consistent with myocardial infarction or unstable angina as defined by the manufacturer
Cholesterol (fasting)				
Adult ≥ 18 years	200 – 239 mg/dL 5.18 – 6.19 mmol/L	240 – 300 mg/dL 6.20 – 7.77 mmol/L	> 300 mg/dL > 7.77 mmol/L	NA
Pediatric < 18 years	170 – 199 mg/dL 4.40 – 5.15 mmol/L	200 – 300 mg/dL 5.16 – 7.77 mmol/L	> 300 mg/dL > 7.77 mmol/L	NA
Creatine Kinase	$3.0 - 5.9 \text{ x ULN}^{\dagger}$	$6.0 - 9.9 \times ULN^{\dagger}$	$10.0 - 19.9 \times ULN^{\dagger}$	\geq 20.0 x ULN [†]
Creatinine	1.1 – 1.3 x ULN [†]	1.4 – 1.8 x ULN [†]	1.9 – 3.4 x ULN [†]	\geq 3.5 x ULN [†]

LABORATORY				
PARAMETER	GRADE 1	GRADE 2	GRADE 3	GRADE 4
	MILD	MODERATE	SEVERE	VERY SEVERE
Glucose, serum, high				
Nonfasting	116 – 160 mg/dL	161 – 250 mg/dL	251 – 500 mg/dL	> 500 mg/dL
	6.44 – 8.88 mmol/L	8.89 – 13.88 mmol/L	13.89 – 27.75 mmol/L	> 27.75 mmol/L
Fasting	110 – 125 mg/dL	126 – 250 mg/dL	251 – 500 mg/dL	> 500 mg/dL
	6.11 – 6.94 mmol/L	6.95 – 13.88 mmol/L	13.89 – 27.75 mmol/L	> 27.75 mmol/L
Glucose, serum, low				
Adult and Pediatric	55 – 64 mg/dL	40 – 54 mg/dL	30 – 39 mg/dL	< 30 mg/dL
≥ 1 month	3.05 – 3.55 mmol/L	2.22 – 3.06 mmol/L	1.67 – 2.23 mmol/L	< 1.67 mmol/L

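### The sentinel rule can release the next injection before any post-dose CK or troponin I result is known, although a marked related rise in either is an event the rule is meant to exclude

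*Protocol*

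**What the plan says.** - **Release rule (Protocol 5.0, Sentinel recipients).** If no reactogenicity or adverse events that are both related and Grade 3 or 4 "occur within 7 days after injection, the second volunteer may be injected". For the third volunteer, "The same process will be followed after the second injection". The end of the passage on the third volunteer is lost in the extracted text, but the sentence releasing the second is complete. The synopsis and 2.7 add that the separation is at least 7 days.
- **Visit windows (6.3 and Appendix A).** Volunteers return on "Day 3 (+/- 1 day), Day 7 (+/- 3 days), Day 14 (+/- 3 days").
- **Day 3 laboratory panel (9.1.10; Appendix A, footnote 2).** This "visit does not include total bilirubin, alkaline phosphatase, albumin, creatine kinase and all tests listed" under Other in Table 9.1.10-1, a row that includes cardiac troponin I.
- **What counts as an event (10.1).** An adverse event can be "any unfavorable or unintended sign (including an abnormal laboratory finding), symptom, or disease".
- **Grading (Appendix B).** CK is Grade 3 at 10.0 to 19.9 x ULN and Grade 4 from 20.0 x ULN. Troponin I has a Grade 4 entry only: "Levels consistent with myocardial infarction or unstable angina as defined by the manufacturer".
- **Dose escalation (5.0), for contrast.** "Safety data through the Day 42 post-injection visit for all volunteers in the dosage group will be reviewed by the SRB prior to" opening the second dosage group.

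**The concern.** The stagger is there so that product-related events can be seen in one person before the next is injected. The release condition is framed as the absence of an event over 7 days, with no statement of what must have been measured and read to establish that absence. For symptoms this may be enough. For a laboratory event, absence means nothing until the sample has been taken and reported.

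The two markers concerned are the ones this product calls for. Section 2.4 reports no human experience, injection-site muscle inflammation in mice that reached necrosis at its worst, and minimal cardiac inflammation or fibrosis in 3 of 40 mice at the highest dose. The Protocol relies on CK to screen for muscle inflammation and on troponin I, with ECG, for the heart.

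A late result would trigger the pause in 17.4 ("One volunteer develops a Grade 3 or 4 adverse event that is judged to be possibly, probably or definitely related to IMP"), but the next volunteer may already have had a single, irreversible dose. Weekly review by the Protocol Safety Review Team and the Safety Review Board reviews at Days 42 and 56 do not hold the release either.

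**Working it through.** The Protocol gives no figure for this point, so the check is schedule arithmetic and a count.

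**1. What is certain to be available at release**

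| Item | Source | Days after injection |
|---|---|---|
| Day 3 visit | 6.3, 3 ± 1 | 2 to 4 |
| Day 7 visit | 6.3, 7 ± 3 | 4 to 10 |
| Earliest next injection | 5.0 | 7 |

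The Day 7 visit may fall on Day 8, 9 or 10, which is up to 10 − 7 = 3 days after the earliest permitted next injection. If it is held on Day 7 or shortly before, the results may still be pending, and 5.0 does not ask for them. The only post-dose laboratory visit certain to have taken place before Day 7 is Day 3, and it contains neither CK nor troponin I. A fully compliant sequence can therefore have no post-dose result for either.

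**2. Which omitted tests could bear on the rule**

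Tests omitted at Day 3: 4 chemistry (total bilirubin, alkaline phosphatase, albumin, CK) + 6 Other (CRP, troponin I, aPTT, INR, C3, C4) = 10.

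- With an Appendix B Grade 3 or 4 threshold: total bilirubin, alkaline phosphatase, albumin, CK, troponin I, aPTT, INR = 7.
- With no Appendix B grade: CRP, C3, C4 = 3. These could not affect release under the present criterion.

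Since 10.1 makes abnormal laboratory findings adverse events, a related CK of at least 10 x ULN, or a related troponin I at infarction or unstable-angina level, meets the rule's own criterion.

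**3. Number of releases affected**

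Each sentinel group has two releases (first to second volunteer, second to third).

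- C1 path (Groups A, B, C): 2 × 3 = 6.
- D path (Groups A to D): 2 × 4 = 8.

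**4. How often both volunteers are on active product**

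Each group has 3 active and 1 placebo. Assume the placebo is equally likely in each of the four positions. For any two consecutive volunteers:

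P(both active) = 3/4 × 2/3 = 1/2.

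The expected number of releases with both active is 6 × 1/2 = 3 on the C1 path and 8 × 1/2 = 4 on the D path.

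**5. Delay if the Day 7 results are awaited**

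The latest Day 7 visit is Day 10, so the delay is at most 10 − 7 = 3 days plus laboratory turnaround. The turnaround time is not given.

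**The case against.** The strongest reply is that this reads the rule too permissively. Someone must establish that no event occurred. The Memory Aid runs for 7 days, reactogenicity is assessed at Days 3 and 7, 2.7 lists safety laboratories at both visits, and 7 days is a minimum. A sensible investigator would wait for the Day 7 assessment, and the Study Operations Manual, which is not shown, may require it. That may describe practice, but a minimum interval does not make a result a condition of release, and the Protocol text allows release without one.

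Second, the consequence is remote. Peak expression is put at about 4 weeks at the earliest, and the cardiac finding in mice was minimal, at 100-fold the highest planned human dose per kg. Day 3 already gives ECG, AST/ALT, creatinine, haematology, urinalysis and a symptom review. Harm needs a late visit or pending result, a marked related rise, no other early signal, and an active next recipient. This stands as a limit on severity: the gap is partial and its frequency unknown. But none of the Day 3 tests replaces CK or troponin I, and the Protocol itself schedules both at Day 7.

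Third, part of the sentinel text is damaged in extraction, both in 5.0 and in the synopsis. The sentence releasing the second volunteer is intact, so the point does not rest on the missing words. The count of two releases per group does rely on the same process applying after the second injection.

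Last, the final summary of changes says enrolment is complete. That limits what an amendment could now change in this trial. It does not make the rule sound.

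**Conclusion.** The concern holds. As written, the sentinel rule can be satisfied with no post-dose CK or troponin I result from the preceding volunteer, although both have thresholds within the rule's Grade 3 or 4 criterion. It applies to six releases on the C1 path or eight on the D path. On the equal-position assumption for placebo, the preceding and next volunteers are both active in an expected 3 of 6 or 4 of 8. At worst, one further healthy volunteer is exposed per release before the pausing rule can act.

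The conclusion rests on the windows in 6.3 and Appendix A, the Day 3 omission in 9.1.10, and the grades in Appendix B. It does not assume that a Grade 3 or 4 rise in the first week is likely, or that late Day 7 visits are common; the document supports neither estimate. The change should be made, but this is a partial gap and not a failure of the whole stagger.

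**What to change.** In 5.0 and the synopsis, release the next injection at the later of (a) 7 days and (b) completed review of the preceding volunteer's Day 7 visit, covering reactogenicity, ECG and safety laboratories including CK and troponin I. The Grade 3 or 4 threshold can stay.

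An alternative is to hold the sentinels' Day 7 visit early enough for its results to be reviewed by Day 7. This is weaker, because it shortens the period observed before the sample is taken.

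The cost is one sentence in each place and up to about 3 days plus laboratory turnaround per step, over six or eight releases. No new visit or test is needed.

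As an editorial follow-on, correct 2.7, which has troponin I measured at every scheduled visit, to agree with the Day 3 omission in 9.1.10.

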5.1 Duration of the Study

Volunteers will be screened up to 42 days before injection and will be followed for 12 months after the single administration.

It is anticipated that it will take approximately 13 months to enrol the study. The anticipated study duration for each volunteer is approximately 13 months from screening through last study visit.

Upon completion of this study, volunteers will be asked to participate in a follow up study to assess safety and PG9 expression for at least 4 additional years.

5.2 Study Population

The study population consists of healthy male adults aged 18 to 45 years who are willing to undergo HIV testing, and who, in the opinion of the investigator or designee, understand the study and provide written informed consent.

Up to 24 volunteers (18 active/6 placebo recipients) who meet all eligibility criteria will be included in the study.

5.3 Inclusion Criteria

- 1. Healthy male, as assessed by a medical history, physical exam, and laboratory tests
- 2. At least 18 years of age on the day of screening and has not reached his 46th birthday on the day of injection
- 3. Willing to comply with the requirements of the protocol and available for follow-up for the planned duration of the study
- 4. In the opinion of the Principal Investigator or designee and based on Assessment of Informed Consent Understanding results, has understood the information provided and potential impact and/or risks linked to injection and participation in the trial; written informed consent will be obtained from the volunteer before any study-related procedures are performed
- 5. Willing to undergo HIV testing, risk reduction counselling and receive HIV test results
- 6. All sexually active males must be willing to use male condoms with all sexual partners (female or male) from the day of first injection until 3 months after the injection
- 7. Willing to forgo donations of blood, or any other tissues during the study and, for those who test HIV-positive due to IMP-induced antibodies, until the anti-HIV antibody titres become undetectable
- 8. Group D1 only: Willing to undergo muscle biopsy 3 months and 12 months after receiving rAAV1-PG9DP or placebo.

